10.1.2 Reporting and description of adverse events

In order to ensure complete safety data collection, all ADRs and AESIs (Section 10.1.8) occurring during the study (ie, after signing the Patient Data Consent form or after first administration of the study drug, whatever comes first) must be reported. This includes all ADRs and AESIs not present prior to the initial visit and all ADRs and AESIs that recurred or worsened after the initial visit (eg, underlying or previous concomitant disease).

Signs or symptoms of the condition/disease for which the study treatment is being studied should be recorded as ADRs or AESIs only if their nature changes considerably or their frequency or intensity increases in a clinically significant manner as compared to the clinical profile known to the treating physician from the patient's history or the Baseline Period.

When recording an ADR or AESI, the treating physician should use the overall diagnosis or syndrome using standard medical terminology, rather than recording individual symptoms or signs. The Adverse Event Report form and source documents should be consistent.

Details for completion of the Adverse Event Report form are described in the AE reporting instructions.

10.1.3 Follow up on adverse events

An ADR or AESI should be followed until it has resolved, has a stable sequelae, the treating physician determines that it is no longer clinically significant, or the patient is lost to follow up.

If an ADR or AESI is still ongoing at the end of the study for a patient, follow up might be requested by local UCB's Drug Safety department, depending on the nature of the ADR/AESI. Follow up should be provided until resolution/stable level of sequelae, the treating physician no longer deems that it is clinically significant, or until the patient is lost to follow up (ie, cannot be contacted). If no follow up is provided, the treating physician must provide a justification.

10.1.4 Pregnancy

If a treating physician is notified that a patient has become pregnant after the first intake of LCM, the treating physician must notify UCB's local Drug Safety department immediately (a Pregnancy Report and Outcome form will be provided to the treating physician for completion). The treating physician shall inform the patient of the information currently known about potential risks and about available treatment alternatives.

The pregnancy and the outcome (birth, miscarriage, abortion) will be documented on the Pregnancy Report and Outcome form provided to the treating physician. The progression of the pregnancy and the eventual birth (if applicable) must be followed up using the Pregnancy Report and Outcome form in which the treating physician has to report on the health of the mother and of the child. Every reasonable attempt should be made to follow the development and health of the child for at least 30 days after birth for any significant medical issues or developmental delay.

If the patient is lost to follow up and/or refuses to give information, written documentation of attempts to contact the patient needs to be provided by the treating physician and filed at the site. UCB's local Drug Safety department is the primary contact for any questions related to the data collection for the pregnancy, birth, and follow up.

In cases where the partner of a male patient enrolled in a NIS becomes pregnant, the treating physician or designee is asked to contact the patient to request consent via the Partner Pregnancy Consent form. In case of questions about the consent process, the treating physician may contact UCB's local Drug Safety department. The treating physician will complete the Pregnancy Report and Outcome form and send it to UCB's local Drug Safety department only after the partner has agreed that additional information can be captured and has provided the signed Partner Pregnancy Consent form. UCB's local Drug Safety department is also the primary contact for any questions related to the data collection for the partner pregnancy, eventual birth, and follow up.

10.1.5 Overdose of lacosamide

Excessive dosing (beyond the maximal allowed dose according to marketing authorization) should be reported on the Adverse Event Report form, whether the overdose is associated with an ADR/AESI or not. Any ADR associated with excessive dosing must be followed as any other ADR would be followed.

10.1.6 Safety signal detection

Reported ADRs or AESIs from this study will be reviewed periodically together with other safety information received at UCB, to detect as early as possible any safety concern(s) related to the treatment so that treating physicians, clinical study patients, and regulatory authorities will be informed appropriately and as early as possible.

10.1.7 Procedures for reporting adverse events and adverse drug reactions

The patient will be given the opportunity to report AEs spontaneously. A general prompt will also be given at each study visit to detect AEs. For example:

“Did you notice anything unusual about your health (since your last visit)?”

Following a causality assessment, the physician will document all spontaneously reported ADRs by the patient in the Adverse Event Report form. In addition, the treating physician should review any self-assessment procedures employed.

If an ADR or AESI is reported, UCB's local Drug Safety department must be informed within 1 working day of receipt of this information by the site (see contact details for safety reporting on the Study Contact Information page of this NIS observational plan). The treating physician must forward to UCB (or its representative) a duly completed Adverse Event Report form provided by UCB, even if the data are incomplete, or if it is obvious that more data will be needed in order to draw any conclusions. Information recorded on this form will be entered into the global safety database.

If clarifications on the ADR or AESI are necessary, UCB shall request additional information from the treating physician.

The Adverse Event Report form and other requested information must be provided in English.

Additional information (eg, autopsy or laboratory reports) received by the treating physician must be provided within 24 hours. All documents in the local language must be accompanied by a translation in English, or the relevant information included in the same document must be summarized in the Adverse Event Report form.

The treating physician is specifically requested to collect and report to UCB (or its representative) any ADRs or AESIs (Section 10.1.8), and to also inform participating patients of the need to inform the treating physician of any AE during the study.

At the conclusion of the study, ADR or AESI data will be extracted from the global safety database and will be analyzed along with the clinical data to allow for the final summary of the safety variables (see Section 11.3.4). The current Summary of Product Characteristics for LCM should be considered for the evaluation of ADR expectedness.

10.1.8 Adverse events of special interest

An AESI is any AE that a regulatory authority has mandated to be reported on an expedited basis, regardless of the seriousness, expectedness, or relatedness of the AE to the administration of a UCB product/compound.

The following are the LCM AESIs:

- The following arrhythmias: atrial fibrillation/flutter, ventricular tachycardia or fibrillation, atrioventricular block (second degree, Type I and II, and third degree), and marked bradycardia (<45 beats/min)
- Syncope or loss of consciousness (other than seizure related)
- Serious suspected multiorgan hypersensitivity reactions

Serious suspected multiorgan hypersensitivity cases may be identified and reported to the sponsor by the treating physician using the following algorithm as agreed with the US Food and Drug Administration:

- An AE or laboratory value (as defined in the following text) suggestive of internal organ involvement (including but not limited to hepatitis, nephritis, pneumonitis, carditis,

colitis, encephalitis, pancreatitis, myositis, arthritis, or hematologic system involvement) combined with at least 1 of the following: fever, rash, lymphadenopathy, or eosinophilia.

- Treatment-emergent abnormal laboratory value criteria suggestive of internal organ involvement or eosinophilia:
 - Eosinophils % $\geq 10\%$
 - Eosinophils absolute $\geq 0.5\text{G/L}$
 - Neutrophils absolute $< 1.5\text{G/L}$
 - Platelets $\leq 100\text{G/L}$
 - Alanine aminotransferase $\geq 2\times$ upper level of normal (ULN)
 - Aspartate aminotransferase $\geq 2\times\text{ULN}$

11 STATISTICS

A description of statistical methods is presented below and will be described in more detail in the Statistical Analysis Plan.

11.1 Definition of analysis sets

For this NIS, the following definitions will apply:

The Enrolled Set (ES) is defined as all patients included in the study and for whom at least Visit 1 is documented. The ES will be used for patient disposition and patient data listings only.

The Safety Set (SS) is defined as all patients included in this study receiving treatment with LCM at least once in the study. The SS will be used for the analysis of the retention and discontinuation rates, time to discontinuation, safety data, and Baseline characteristics of the patients.

The Full Analysis Set (FAS) is defined as all patients in the SS who have at least 1 post-Baseline PGIC or seizure assessment. The FAS will be used for the analysis of the primary and most secondary variables.

The modified FAS is defined as all patients in the FAS ≥ 16 years of age and treated with daily LCM doses $\leq 400\text{mg}$, representing the on-label use of LCM.

11.2 General statistical considerations

All variables will be summarized using descriptive statistics; there will be no inferential analyses. For continuous variables, summary statistics (number of available observations, mean, standard deviation, minimum, median, and maximum) will be tabulated. Categorical variables will be summarized by the number of patients and the percent of patients in each category. For time to event variables, medians derived using Kaplan-Meier estimates and corresponding 95% confidence intervals (CIs) will be presented.

Data from patients who prematurely withdraw from the study will be analyzed up to the final visit attended.

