8.2 Withdrawal criteria

Patients are free to withdraw from the study at any time, without prejudice to their continued care.

Physicians are free to add or withdraw any medication or to withdraw the patient from the study at their own discretion.

If a patient needs to increase the dose of the Baseline AEDs (1 or 2) or needs to be treated with more than 2 AEDs other than LCM, these changes can be implemented, but the patient will be withdrawn from the study.

If the physician elects to stop LCM treatment, the patient will be withdrawn from the study.

The primary reason for withdrawal must be documented in the patient's eDF. When the primary reason for withdrawal is an ADR, the ADR must be reported as described in Section [10.1.7](#).

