^c Patients who discontinue early should perform Visit 3 assessments as a Withdrawal Visit.

^d During the previous 8 weeks and relevant information in the past according to the physician's decision.

^e The treating physician will evaluate at each visit, as part of standard practice with the patient, the frequency and type of seizures experienced by the patient since the previous study visit.

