3.2 General study level definitions

3.2.1 Analysis time points

The following visits are recommended documentation time points and will be considered for analysis. Due to the nature of a NIS, the time points given for each visit are approximated, expected time points only.

- Visit 1, Baseline
- Visit 2 (approximately 3 months after Baseline): Visits that occurred \leq 135 days after Visit 1
- Visit 3 (approximately 6 months after Baseline or Withdrawal Visit for patients who discontinue early): All visits that occurred $>$ 135 days after Visit 1

If there are 2 visits that meet the criteria for Visit 2, then the visit nearest to the scheduled assessment time for Visit 2 will be used (i.e. 90 days after Visit 1). If there are 2 visits that meet the criteria for Visit 3, then the visit nearest to the scheduled assessment time for Visit 3 will be used (i.e. 180 days after Visit 1). No different study periods will be considered for this NIS.

However, the period for the analysis of safety variables is defined as follows:

- Observational Period: The Observational Period starts with the start date of LCM and ends at the day of study termination. In case the start date of LCM is missing, the date of Visit 1 will be used instead.

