3.2.2 End date of the Observational Period

The end date of the Observational Period will be the date of Visit 3, which is approximately 6 months after Baseline for subjects completing the Treatment Period, or the Withdrawal Visit for subjects who discontinued during the Observational Period. If a subject does not have a Visit 3 for any reason including death, then either the date of early withdrawal or the date of last known dose of study drug during the Observational Period, whichever is later, will define the end date of the Observational Period.

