3.10.4 Seizure Frequency

Partial-onset seizure frequency per 28 days will be derived from the number of days in the considered time interval (D) for which seizure information was provided:

$$(\text{Number of seizures over the specified time interval}) \times (28/D)$$

The considered time interval is defined as 56 days for the historical seizure count at Baseline (8 weeks x 7 days) and as date of actual visit – date of previous visit for all other time points. Note

if any subjects have a diagnosis of epilepsy less than 8 weeks prior to study entry, then site will be instructed to give their best approximation of the 8-week seizure frequency and the reported historical seizure count will be assumed to be representative of the full 8 weeks. The seizure frequency per 28 days cannot be derived using the time from diagnosis of epilepsy to study start as the time period for reporting the historical seizure frequency for such subjects because only the month and year are collected for the date of diagnosis.

The absolute and percentage change in partial-onset seizure frequency from Baseline (Visit 1) will be derived for Visit 2 and Visit 3.

A responder is defined as a patient who experiences a 50% or greater reduction in partial-onset seizure frequency from Visit 1 (Baseline) to Visit 3 (Month 6 or end of Observation Period).

The seizure-free status (Yes/No) at the end of the 6-month Observation Period will be determined for each patient. A patient is seizure-free if the seizure count at Visit 3 (Month 6 or end of the Observation Period) is 0, otherwise the patient is not seizure-free at the end of the 6-month Observation Period.

The frequency of seizures with and without secondary generalization will also be calculated based upon the response to the question 'Number of partial-onset seizures with secondary generalization' in the CRF. If the number with secondary generalization is known, the number of seizures with secondary generalization will be taken from the CRF and the number of seizures without secondary generalization will be calculated as overall number of seizures – number of seizures with secondary generalization.

Partial-onset seizure frequency per 28 days at a dose of <200mg/day at Visit 2 and Visit 3 will be derived from the number of days in the considered time interval (D) for which seizure information was provided where the subject was on a dose of <200mg/day according the dosing log for LCM:

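### A patient withdrawn because a Baseline AED was increased or more than 2 AEDs other than LCM were needed can still count as a responder or as seizure-free, and no rule counts that patient as a failure.

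*Protocol*

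**What the plan says.** **Withdrawal.** Under Protocol 8.2, when a patient needs a higher dose of a Baseline AED or more than 2 AEDs other than LCM, "these changes can be implemented, but the patient will be withdrawn from the study". Stopping LCM is a separate trigger: "If the physician elects to stop LCM treatment, the patient will be withdrawn from the study". A withdrawal for AED change therefore does not require LCM to have stopped.

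**Assessment at withdrawal.** Protocol section 5 and Table 15-1 footnote c: "Patients who discontinue early should perform Visit 3 assessments as a Withdrawal Visit". SAP 3.2.2 ends the Observational Period at Visit 3 "or the Withdrawal Visit for subjects who discontinued during the Observational Period".

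**Use of the data.** Protocol 11.2, repeated in SAP section 4: "Data from patients who prematurely withdraw from the study will be analyzed up to the final visit attended". The reason for leaving plays no part.

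**Scoring.** SAP 3.10.4: "A responder is defined as a patient who experiences a 50% or greater reduction in partial-onset seizure frequency from Visit 1 (Baseline) to Visit 3", where Visit 3 means Month 6 or the end of the Observation Period. Seizure-free status needs only a zero count at Visit 3. The post-Baseline interval is the visit date minus the previous visit date. SAP 8.1.2.1 bases percentages on patients with available data, and SAP 4.2 does not substitute missing values.

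**Visit windows.** SAP 3.2.1 names the Withdrawal Visit as Visit 3. It also assigns visits up to day 135 to Visit 2 and only later ones to Visit 3.

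**The concern.** The primary objective is the effectiveness of LCM added to 1 or 2 AEDs. Once more than 2 other AEDs are in use, the patient is on a regimen outside that objective. Once a Baseline AED has been increased, the seizure count mixes the effect of LCM with that of another drug's dose. The protocol ends participation at that point, but the responder and seizure-free definitions do not register it. Visits follow routine practice, so the last interval can run past the change, and any improvement after it is credited to LCM.

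Nothing elsewhere closes the gap. SAP 3.4 uses no Per-Protocol Set. The FAS needs only one post-Baseline PGIC or seizure assessment, and the modified FAS filters only on age and LCM dose. SAP 3.10.7 appears to treat early withdrawals as events for retention, so one patient could be both a retention failure and a responder.

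**Working it through.** **1. The plan's own figure.** Protocol 11.5 and SAP 2.4 expect a 60% responder rate with a 95% CI of about ±10 points. n = 1.96² × 0.60 × 0.40 / 0.10² = 92.2, rounded up to 93. The half-width at 93 is 1.96 × √(0.24/93) = 0.0996. 93/0.93 = 100 enrolled. The figure reproduces and is not in question; it gives the scale for what follows.

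**2. A patient after day 135 (illustrative counts).** Baseline: 4 seizures in 56 days, so 4 × 28/56 = 2.0 per 28 days. Visit 2 is on day 90. A Baseline AED is then increased, and the Withdrawal Visit falls on day 150 with 2 seizures in 60 days, so 2 × 28/60 = 0.93 per 28 days. The reduction is (2.0 − 0.93)/2.0 = 53.3%. The visit is past day 135, so it is Visit 3 under both the SAP window and the Withdrawal Visit label. The patient is a responder on every reading. With 0 seizures in those 60 days the patient would also be seizure-free.

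**3. The same counts by day 135.** Put the Withdrawal Visit on day 60 with no earlier Visit 2. Under the protocol, SAP 3.2.2 and the label in SAP 3.2.1, this visit is Visit 3 and the patient is again a responder (53.3%). Under the SAP 3.2.1 window it is Visit 2, there is no Visit 3 value, and the patient leaves the available-data denominator.

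**4. How often might such a patient meet the 50% rule?** Assumed model: Baseline count B in 56 days, daily rate r = B/56, no LCM effect, an AED change that halves the rate, and a last interval D = 90 days. The patient is a responder if X ≤ floor(0.5 × B × 90/56), with X Poisson and mean r × (days before the change) + 0.5 × r × (days after). The thresholds are 0, 1, 3 and 6 seizures for B = 1, 2, 4 and 8.

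| Days of the 90 after the change | B=1 | B=2 | B=4 | B=8 |
|---|---|---|---|---|
| 0 | 20% | 17% | 12% | 3% |
| 14 | 23% | 21% | 16% | 5% |
| 45 | 30% | 31% | 29% | 15% |
| 90 | 45% | 52% | 60% | 54% |

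**5. Effect on the responder rate if these patients are scored.** Excess over counting them as non-responders = share withdrawn × share meeting the rule. Both shares are assumptions: 5-20% and 3-50%.

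| Share withdrawn | 3% meet the rule | 50% meet the rule |
|---|---|---|
| 5% | 0.15 points | 2.5 points |
| 10% | 0.3 points | 5 points |
| 20% | 0.6 points | 10 points |

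The last row of the table in step 4 reaches 60%, which at 20% withdrawn would give 12 points. It needs the AED change at the previous visit and a further 90 days before the Withdrawal Visit.

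**6. In patients.** Take 56/93 = 60.2% responders, of whom 4 are among 9 AED-change withdrawals. Counting those 9 as non-responders gives 52/93 = 55.9%, which is 4.3 points lower. If all 9 left by day 135 and the window drops them, the reported rate is 52/84 = 61.9%, which is 6.0 points above 55.9%. Dropping them is therefore not a neutral alternative.

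**The case against.** The strongest reply is that this is a descriptive single-arm study, that analyzing observed data to the last visit is a stated and transparent rule, and that these patients are not hidden. Disposition tabulates the reasons for termination, retention handles early withdrawals, and discontinuation for lack of efficacy has its own rate and CI. That holds as far as it goes, but none of these outputs adjusts the responder or seizure-free rate.

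Four stronger readings are tempting, and the documents do not support them:

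- *Every such patient is scored at the Withdrawal Visit.* This is certain only after day 135. Before that, the SAP 3.2.1 window may remove the patient instead.
- *These are add-on failures who stay on LCM.* Protocol 8.2 says that the patient needs the change. It does not say that seizure control was the reason or that LCM continues; LCM can continue.
- *The bias is around 10 points.* If the change is decided at the visit that becomes the Withdrawal Visit, the whole interval precedes it, and the model gives 3-20% responders. With 14 days after the change it gives 5-23%. No passage states a typical lag.
- *The headline definition must be replaced.* That would score as failures even patients whose reduction came entirely before the change. An added analysis answers the point without that cost.

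It is also fair to object that the seizure interval cannot simply be cut at the AED change. Table 15-1 footnote e collects seizure frequency and type since the previous visit, and no passage shows dated seizures.

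**Conclusion.** The gap is real and affects a primary variable. As written, the plan lets a patient withdrawn for AED change after day 135 count as a responder or as seizure-free. For one withdrawn by day 135, it leaves open whether the patient is scored or dropped. On neither reading is the AED change treated as a failure.

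For patients who are scored, the responder rate is about 0.2 to 10 points higher than if they were counted as non-responders. This rests on the two assumed shares, 5-20% withdrawn and 3-50% meeting the rule. The low end applies when the Withdrawal Visit coincides with the AED change. The high end needs both many such withdrawals and a long interval after the change. Against that comparator the difference cannot be negative. The stated precision is about ±10 points.

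The sample size of 93 is unaffected, and no test or error rate is at stake. A patient on 1 Baseline AED who adds a second one is not withdrawn under Protocol 8.2 and is outside this point.

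**What to change.** 1. In SAP 3.10.4, 8.1.2.1 and 8.2.6, pre-specify an analysis of the responder and seizure-free rates that counts as non-responder and not seizure-free every patient withdrawn for a Baseline AED increase or for more than 2 AEDs other than LCM. Include those withdrawn by day 135, so that they stay in the denominator.
2. Report this analysis, and the number of such patients, beside the observed-data rate.
3. Reconcile SAP 3.2.1 with SAP 3.2.2 on which visit is Visit 3 for early withdrawals.
4. Do not plan an analysis that ends the seizure interval at the AED change unless dated seizures are available.

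The cost is SAP text and programming. AEDs are recorded at Visits 1, 2 and 3, and the primary withdrawal reason is in the eDF. The only termination reasons that the SAP definitions name are adverse drug reaction and lack of efficacy, so the patients will probably have to be identified from the AED records together with the withdrawal reason. The downside is a somewhat lower rate in the added analysis. No clinical withdrawal rule changes.
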